7.2. Patient Accountability

This section will describe patient accountability, overall and by treatment. Bar charts will be used for the presentation.

7.3. Baseline Characteristics

This report displays treatment group comparisons for baseline variables including medical history and socio-demographic information. Bar charts for categorical variables and boxplots for continuous variables will be used for the presentation of baseline characteristics.

7.4. Assessments at the ED Visit

This section will include a scatterplot of pain assessment results at the ED Visit from ED bed placement to reach time point of every 30 minute over time, overall and by treatment. It will also include bar charts per question over time, regarding pain relief, change in pain, and pain medicine. Bar charts in the same format will be displayed for nausea, vomiting, and pruritus, including results at ED bed placement. Box plots of blood pressure, heart rate, SpO₂, sedation score, and respiration rate will also be presented, including results at ED bed placement.

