12.5.1 Protocol-Specific AEs

The following events are considered expected AEs for this protocol and are reported on the AE eCRF.

- Nausea
- Vomiting
- Pruritis
- SPO₂ < 95 % requiring supplemental use of oxygen via nasal cannula due to opioid therapy
- Moderate or severe sedation
- Drowsiness
- Respiratory depression not requiring intubation or naloxone
- Low blood pressure

AEs are summarized and reported to DSMB in bi-annual meetings.

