7.6. Safety Outcomes

This section contains bar chart displays of protocol-specific expected adverse event (AE) data, such as nausea, vomiting, puritis, SPO₂ < 95% requiring supplemental oxygen via nasal cannula due to opioid therapy, moderate to severe sedation, drowsiness, respiratory depression not requiring intubation, and low blood pressure.

This section also contains bar chart displays of the incidence of protocol-specific serious adverse events (SAE), including respiratory depression requiring naloxone administration given within the 2 hours of last administration of pain protocol drug, any event resulting in death, any event that is considered a life-threatening complication, any event requiring admission to the intensive care unit (ICU), any event requiring intubation, and hospitalizations with the primary reasons.

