14. ADVERSE AND SERIOUS ADVERSE EVENTS (TABLES)

14.1. Adverse Events

	Treatment A N=	Treatment B N=	Total N=	P-value
Nausea				
Vomiting				
Pruritis				
SPO₂ < 95% requiring supplemental oxygen via nasal cannula due to opioid therapy				
Moderate to Severe Sedation (Sedation Score of > 3)				
Drowsiness				
Respiratory Depression not requiring intubation				
Low Blood Pressure (SBP < 90mmHg and/or DBP < 50 mmHg)				

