14.2. Serious Adverse Events

	Treatment A N=	Treatment B N=	Total N=	P-value
Respiratory depression requiring naloxone administration given within the 2 hours of last administration of pain protocol drug Mild Moderate Severe Total				
Any event resulting in death Mild Moderate Severe Total				
Any event that is considered a life-threatening complication Mild Moderate Severe Total				
Any event requiring admission to the Intensive Care Unit (ICU) Mild Moderate Severe Total				
Any event requiring intubation Mild Moderate Severe Total				

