16. ASSESSMENTS AT ED VISIT (TABLE)

16.1. Assessments

	Treatment A N=	Treatment B N=	Total N=
Pain Score 30 min 60 min 90 min 120 min 150 min 180 min 210 min 240 min 270 min 300 min 330 min 360 min			
Blood Pressure (SBP) 30 min 60 min 90 min 120 min 150 min 180 min 210 min 240 min 270 min 300 min 330 min 360 min			
Blood Pressure (DBP) 30 min 60 min 90 min 120 min 150 min 180 min 210 min 240 min 270 min			

300 min 330 min 360 min			
Heart Rate (RR) 30 min 60 min 90 min 120 min 150 min 180 min 210 min 240 min 270 min 300 min 330 min 360 min			
SpO2 30 min 60 min 90 min 120 min 150 min 180 min 210 min 240 min 270 min 300 min 330 min 360 min			
Sedation Score (0-4) 30 min 60 min 90 min 120 min 150 min 180 min 210 min 240 min 270 min 300 min 330 min 360 min			

Respiration Rate (RR)			
30 min			
60 min			
90 min			
120 min			
150 min			
180 min			
210 min			
240 min			
270 min			
300 min			
330 min			
360 min			

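### No planned display reports how many patients per arm had a low respiration rate or SpO2 after dosing, although both are read every 30 minutes.

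*SAP*

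**What the plan says.** **Collection.** Protocol 8.3, Table 2 has the research assistant record sedation level, SpO2, blood pressure, heart rate and RR every 30 minutes in both arms. Under Protocol 6.2 the assistant doing the assessments is blinded to arm.

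**Display of the readings.** SAP 7.4 plans box plots: blood pressure, heart rate, SpO2, "sedation score, and respiration rate will also be presented, including results at ED bed placement". SAP 10.4 to 10.6 plan one figure per sign over time. Table 16.1 has one row per time from 30 to 360 minutes, for example under "Respiration Rate (RR", and no row for a patient's lowest value.

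**Patient counts by arm.** These are the AE and SAE rows described in SAP 7.6 and laid out in Tables 14.1 and 14.2:
- SpO2 below 95%, listed in SAP 7.6 as "requiring supplemental oxygen via nasal cannula due to opioid therapy, moderate to severe sedation, drowsiness, respiratory depression not requiring intubation, and low blood pressure" (the same sentence names the other AE rows);
- "Respiratory Depression not requiring intubation", which Protocol 12.5.1 words as "Respiratory depression not requiring intubation or naloxone";
- moderate to severe sedation, defined as "Sedation Score of > 3";
- in Table 14.2, "Respiratory depression requiring naloxone administration given within the 2 hours of last administration of pain protocol drug".

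For contrast, the blood pressure row of Table 14.1 does carry numeric limits: "Low Blood Pressure (SBP < 90mmHg and/or DBP < 50 mmHg".

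**The concern.** Protocol 12.4 names respiratory depression as a less common side effect of the study opioids, and the two arms differ by design in dose. RR and SpO2 are the objective signs of that risk, and a blinded assistant records them. Yet the planned counts by arm rest on an event being recognised and entered on a form, and two of the rows also need a treatment: oxygen or naloxone. Protocol 6.2 says the ED provider is unblinded (SAP 3.2 agrees; SAP 2.3 says the emergency physician is blinded). A count taken directly from the readings would not depend on that decision.

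At stake is one plain safety statement: how many patients in each arm had a low RR or SpO2 after dosing. A brief low reading that was neither treated nor entered as an event would appear in the data but in no patient count.

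**Working it through.** **1. What each display can show.**

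| Display | Unit | Number of patients with a low reading? |
|---|---|---|
| Box plots, figures (SAP 7.4, 10.4, 10.6) | value at each time; whiskers end at the 5th and 95th percentiles (SAP 6.3.2) | No |
| Table 16.1 | summary at each time, among non-missing values (SAP 7.1) | No |
| Minimum and maximum (Protocol 13.6) | one extreme value per summary | No |
| SpO2 row, Table 14.1 | patients, if oxygen was required due to opioid therapy | Treated cases only |
| Respiratory depression row, Table 14.1 | patients, no rate named | Recognised events only |
| Naloxone row, Table 14.2 | patients given naloxone | Treated cases only |

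**2. Can by-time percentages be turned into a patient count?** Inputs: 230 patients with ED visits (SAP 2.4), so 230/2 = 115 per arm; 12 times (Table 16.1). The share low at each time, p, is an assumption, because the documents give none; every patient is taken to have all 12 readings.
- Same patients low every time: 115p
- Independent across times: 115(1 − (1 − p)^12)
- Different patients each time: 115 × 12p

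| p | same | independent | all different |
|---|---|---|---|
| 1% | 1.2 | 13.1 | 13.8 |
| 2% | 2.3 | 24.8 | 27.6 |
| 5% | 5.8 | 52.9 | 69.0 |

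With 9 readings and p = 2% the range is 2.3 to 20.7. One by-time picture fits patient counts that differ about twelvefold (ninefold with 9 readings).

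**3. Would printed minima help?** Simulation, all inputs assumed: 115 patients, 8 readings, RR mean 18, between- and within-patient SD 1.8 each, low value 8; a by-time minimum of 8.5 or less counts as low. Share of runs with a low minimum at 7 or more of the 8 times:
- 1 patient low throughout (0.9%): 100%
- 4 patients with six lows each (3.5%): 96%
- 12 patients with two lows each (10.4%): 94%
- 24 patients with one low each (20.9%): 97%

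The minima look alike whether 1 or 24 patients are affected. They are not blind to a difference, though: with two consecutive lows in 10% v 2% of patients, minima are low at 7.43 v 3.59 of 8 times, and at more times in the higher-risk arm in 95% of runs.

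**4. What a patient count would report.** Illustration: 12/115 = 10.4% v 3/115 = 2.6%, a difference of 7.8 points. Wilson limits are 6.1 to 17.4% and 0.9 to 7.4%. Newcombe interval:
- lower: 7.8 − √((10.4 − 6.1)² + (7.4 − 2.6)²) = 1.4
- upper: 7.8 + √((17.4 − 10.4)² + (2.6 − 0.9)²) = 15.0

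**5. Why count new crossings only.** If a share q of each arm is already low at placement and new lows occur in 10% v 2% of the rest, an unflagged count compares q + 0.10(1 − q) with q + 0.02(1 − q). At q = 5% that is 14.5% v 6.9%. Exact Fisher power, two-sided 0.05:

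| q | unflagged, 115 per arm | new lows only |
|---|---|---|
| 5% | 38% | 64% (109 per arm) |
| 10% | 27% | 61% (104 per arm) |
| 20% | 16% | 53% (92 per arm) |

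**6. Effect of unequal stays.** Pilot stays were 302 (SD 70) v 254 (SD 79) minutes, patient-specific v weight-based (Protocol Table 3, 26 per arm). Subtracting an assumed wait of 0 to 60 minutes and capping at 360 gives on average 7.5 to 9.4 v 6.0 to 7.9 readings per patient. At an equal 1% risk per reading, 1 − 0.99^k is 7.3% v 5.8% with the long wait and 9.0% v 7.6% with none. With equal risk and a 30-minute wait, Fisher's test on any low reading rejects in 5.7% of runs at 2% risk per reading and 8.4% at 3%; the log-rank test rejects in 5.2% and 5.4%.

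**The case against.** The strongest reply is that the main harms are already counted. Tables 14.1 and 14.2 give patients by arm, with p-values, for low SpO2 with oxygen, respiratory depression, sedation, drowsiness, naloxone use, ICU admission and intubation, and SAP 4.3 names the tests. Clinically defined events are a legitimate safety measure, and no rule in the documents requires a second one based on readings. That stands, and it keeps this point small.

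Other parts of the reply also stand. The AE form is not in the documents, so it may prompt an entry for a low reading or carry a rate limit that the table shell omits. Every rate used above is assumed. By-time minima, if printed, would probably show a marked difference between arms. SAP 7.4 already includes placement values in the box plots. The DSMB and the steering committee review safety during the trial.

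Sedation needs separate treatment. A score-based row by arm already exists, so the gap there is only the cut-off: above 3 on a 0 to 4 scale counts only a 4, which sits badly with a label covering moderate and severe. An underlined inequality sign may have been lost when the PDF was read.

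A reader might infer that the plan would hide respiratory depression. It would not: untreated cases recognised as events have their own row, and sustained or common depression would show in the by-time displays. A reader might also take Protocol Table 2 to mean that total dose is capped in one arm only. The 25% limit there caps the size of each weight-based dose; no total is stated for that arm either.

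None of this supplies the missing count. Treated or recognised events are a subset of patients with low readings, and by-time summaries do not identify patients.

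**Conclusion.** The point holds for RR and SpO2. Both are recorded every 30 minutes by a blinded assistant, and no planned display reports how many patients per arm had a low value after dosing. For sedation, only the cut-off needs attention.

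The size of any consequence is unknown, because the documents give no rate of low readings. What does not depend on a model of RR is that by-time percentages cannot be converted into a patient count: under the assumed 2% per time and 12 readings, the answer runs from about 2 to 28 of 115. The simulated figures and power values are illustrations.

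This is exploratory safety reporting, worth doing because it is cheap, and it ranks between an optional suggestion and a minor recommendation. The primary analysis is unaffected. The documents do not support reading it as a safety failure or as evidence that event counts will be biased by arm; they even disagree on whether the ED physician is blinded.

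**What to change.** In SAP 7.6, beside Table 14.1, add rows derived from the 30-minute readings taken after the first protocol dose, among patients with at least one such reading. Give n (%) by arm with the arm difference and 95% CI:
- lowest RR below a pre-set limit (for example below 10, to be confirmed by the clinical team before unblinding);
- lowest SpO2 below 95%, regardless of oxygen;
- highest sedation score of 3 or more, shown beside the existing row.

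Count new crossings only, and list separately by arm the patients already past the limit at placement. Report the number of readings per patient by arm. As a check for unequal stays, compare time to first low reading by log-rank, a test SAP 6.2 already names, censored at the last assessment.

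The cost is SAP wording, one derived dataset and a few exploratory rows, with no new data collection. The downside is that a count of patients with any low reading depends partly on length of stay. The log-rank check reduces this but does not remove it, since leaving the ED may itself be related to sedation.

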7.5. Dosing

We will present the percentage of agreement between the initial dose assigned and administered dose in a table format.

We will describe overall analgesic dosing by calculating descriptive statistics for the cumulative morphine equivalent dose delivered (total mg, total mg/hr, total mg/kg, and mg/kg/hr), where hr is the number of hours from ED arrival to discharge.

Adjustments of analgesic dose and regimen subsequent to the initial dose are determined by the SCD provider's current observation of the patient. As the CRF does not capture all of the information available to the SCD provider, post hoc analysis of adherence to the dose adjustment plan from study data is challenging.

7.6. Safety Outcomes

This section contains bar chart displays of protocol-specific expected adverse event (AE) data, such as nausea, vomiting, puritis, SPO₂ < 95% requiring supplemental oxygen via nasal cannula due to opioid therapy, moderate to severe sedation, drowsiness, respiratory depression not requiring intubation, and low blood pressure.

This section also contains bar chart displays of the incidence of protocol-specific serious adverse events (SAE), including respiratory depression requiring naloxone administration given within the 2 hours of last administration of pain protocol drug, any event resulting in death, any event that is considered a life-threatening complication, any event requiring admission to the intensive care unit (ICU), any event requiring intubation, and hospitalizations with the primary reasons.

7.7. Study Endpoints

7.7.1. Primary Endpoint

As defined in the protocol, the primary endpoint is “change in pain scores from the time of placement in a treatment area to the time of disposition (hospital admission, discharged home, assigned to observation status) or a maximum treatment duration of 6 hours, whichever comes first.” Comparison of mean changes in pain scores and the difference between treatment arms will be done using linear regression, adjusting for the initial pain score at ED arrival, biological variables of SCD genotype, age and gender. Comparison of unadjusted means will also be done using a t-test. P-value, 95% confidence intervals and the mean difference will be displayed in tabular format. The predicted values will be displayed in a scatter plot by treatment.

Descriptive statistics such as n, mean, standard deviation (SD), median, 25th and 75th percentiles will be also presented for the primary endpoint.

For subgroup analysis of the primary endpoint, in addition to the formal assessment of randomized group by covariate interactions as described in section 4, effects of the treatments will be calculated and displayed (with 95% CI and p-values) for the pre-specified subgroups of patients in both tabular and graphic format. These descriptive summaries will be carefully interpreted in conjunction with the formal interaction tests.

Please refer to section 4 for methods of analysis.

7.7.2. Secondary Endpoints

P-value and descriptive statistics such as n, mean, standard deviation (SD), median, 25th and 75th percentiles and boxplots of summary statistics will be presented for ED length of stay.

P-values, frequencies and percentages by treatment arm will be displayed for hospitalizations for pain control and counts of the return ED visits, hospitalizations, re-hospitalizations, or day hospital visits within seven days of the index ED visit (recorded ED visit). Return ED visits, hospitalizations, re-hospitalizations, or day hospital visits will also be evaluated by collapsing the data into a binary outcome with a cut off at zero after the index ED visit. Bar charts will be used to compare the hospital admission or ED re-admission rates between the two groups. For each patient, the hospitalization rate in the 7-day period following discharge from the ED will be categorized as 0, 1, or 2+. Hospitalization for patients who proceed directly from ED discharge to the hospital will be counted as the first admission/ readmission.

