Treatment Regimen	1:1 treatment allocation will be used with site as the stratification variable. Subjects will be randomized to receive analgesic management for VOE either via a weight-based SCD analgesic, or a patient-specific analgesic developed by their primary SCD outpatient provider.
Blinding	The provider is unblinded in the ED. The patient and research assistants are blinded to study arm.
Objectives:	This phase III randomized clinical trial will identify the best analgesic approach for treating adult SCD patients with VOE during an ED visit. It will determine whether the patient-specific analgesic approach is superior to the weight-based analgesic approach in decreasing the severe pain due to VOE. The trial's results will shape the health care paradigm for the thousands of SCD patients suffering from severe pain.
Primary Endpoint:	Change in pain scores in the ED from the time of placement in treatment area to the time of disposition (hospital admission, discharged home or assigned to observation status) or a maximum treatment duration of 6 hours, whichever comes first
Secondary Endpoints:	
 • ED length of stay • Hospitalization for pain control • Return ED visits • Hospitalizations, if not admitted to hospital on ED visits • Re-hospitalizations, if admitted to hospital on ED visit and was discharged – we ignore those still hospitalized within 7 days of the index ED visits • Day hospital visits, regardless admitted to hospital on ED visits or not • A composite of return ED revisits or hospital re-admissions or day hospital visits (binary outcome with a cutoff at zero)

Location:	6 clinical sites (Emergency Departments (ED)) in the United States
Duration of Treatment	From the time of placement in a treatment area to the time of disposition (hospital admission, discharged home, assigned to observation status) or a maximum treatment duration of 6 hours, whichever comes first.
Duration of Study Overall	The study duration is from the time of placement in a treatment area to Day 7 Post ED Visit. The study enrollment is expected to be 24 months.

ABBREVIATIONS

ACS	Acute Chest Syndrome
ACEP	American College of Emergency Physicians
AE	Adverse Event
CCC	Clinical Coordinating Center
CRF	Case Report Form
DCC	Data Coordinating Center
ED	Emergency Department
EDC	Electronic Data Capture
EMR	Electronic Medical Record
ITT	Intent To Treat
KG	Kilogram
NHLBI	National Heart, Lung and Blood Institute
PI	Principal Investigator

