4.2. Secondary Endpoints

The secondary endpoints are as follows:

- ED length of stay
- Hospitalization for pain control
- Return ED visits
- Hospitalizations, if not admitted to hospital on ED visits
- Re-hospitalizations, if admitted to hospital on ED visit and was discharged – we ignore those still hospitalized within 7 days of the index ED visits
- Day hospital visits, regardless admitted to hospital on ED visits or not
- A composite of return ED revisits or hospital re-admissions or day hospital visits (binary outcome with a cutoff at zero)

Methods of the final analyses: For the ED length of stay (from ED admission to discharge), a linear regression analysis similar to the primary outcome will be used to compare the length of stay between the two arms. For the hospital admission rate, chi-square test will be used to compare the admission rates between the two groups. For the count data (e.g., ED re-visits or hospitalizations or re-hospitalizations, or day hospital visits for VOE within 7 days after the recorded ED visit), it will be first evaluated by collapsing the data into a binary outcome with a cut off at zero and a chi-square test or Fisher exact test (if frequency is below 5 or less) to compare the re-admission rates or rate of a returned ED visit between the two groups. If there is sufficient spread in the count data, a Poisson regression approach will be used to test for protocol differences in the count outcome. (section 13.9.)

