6.2. P-values

Except for the primary, secondary endpoints and safety outcomes for which we pre-specified methods to use in section 4, *P*-values, where applicable, for continuous or ordered categorical data are computed using the nonparametric Kruskal-Wallis test. This test is appropriate for data with non-normal distributions and has power near that of the Student's *t*-test when the data are normal. Pearson's chi-square or Fisher exact is used for dichotomous (e.g., gender) and unordered (e.g., race) categorical data. The log-rank test is used to obtain *p*-values for time-to-event endpoints. Cox modeling will be used for time-to-event outcomes if there are covariates, such as the initial pain score at ED arrival, biological variables of SCD genotype, age and gender.

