12.7. Hospitalizations (if not admitted to hospital on Index ED visit)

[figure not shown]

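### SAP 7.7.2 counts an admission straight from the index ED visit as the first event in the 0/1/2+ count of 7-day hospitalization, against the SAP's own 7-day endpoint definitions

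*SAP*

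**What the plan says.** SAP 7.7.2 states that for each patient "the hospitalization rate in the 7-day period following discharge from the ED will be categorized as 0, 1, or 2" (the top category being 2+). The next sentence gives the counting rule: "Hospitalization for patients who proceed directly from ED discharge to the hospital will be counted as the first admission/ readmission".

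The same section, a few lines earlier, treats index admission for pain as separate from the 7-day events. It lists "hospitalizations for pain control and counts of the return ED visits, hospitalizations, re-hospitalizations, or day hospital visits".

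SAP 4.2 defines two 7-day admission endpoints by index status. One is "Hospitalizations, if not admitted to hospital on ED visits". The other, worded alike in the SAP synopsis, is "Re-hospitalizations, if admitted to hospital on ED visit and was discharged", followed by the instruction that "we ignore those still hospitalized within 7 days of the index ED visits". The figure titles in SAP 12.7 ("Hospitalizations (if not admitted to hospital on Index ED visit") and 12.8 and the rows of Table 17.1 repeat this split. Hospitalization for pain control is an endpoint of its own throughout.

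The protocol (section 11, Secondary Endpoints) also lists hospitalization for pain control apart from the 7-day outcome. Protocol 13.7 gives the two outcomes different rates, both in the R34 results (Table 3) and in the power assumptions.

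**The concern.** A count described as covering the 7 days after the ED visit should show what happened after that visit. Under the 7.7.2 sentence, every patient admitted from the index ED visit starts at 1. The display would then partly repeat an endpoint that is already reported, and it would disagree with the Table 17.1 rows for the same 7 days. A patient with a single return admission could be shown as 2+. Two analysts, one working from 4.2 and one from 7.7.2, would give different values for the same patient.

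**Working it through.** **The two rules, patient by patient**

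| Patient | SAP 4.2 | SAP 7.7.2 count |
|---|---|---|
| Admitted from the index ED visit, still in hospital at day 7 | ignored | 1 |
| Admitted, discharged, no return | 0 | 1 |
| Admitted, discharged, readmitted once within 7 days | 1 | 2+ |
| Not admitted at the index visit, admitted once within 7 days | 1 | 1 |

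The rules agree only for patients who were not admitted at the index visit.

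**Which meaning the protocol's figures carry**

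If direct admissions counted as 7-day events, the 7-day rate could not be lower than the index rate among the same patients.

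- R34 (Protocol 13.7, Table 3): 38.5% index, 9.8% at 7 days. The percentages fit 20/52 and 5/51 (counts inferred). Had direct admissions counted, at least 19 of 51 (37%) would have had a 7-day event, even if the one patient without 7-day data was an index admission.
- Planning rates (Protocol 13.7), patient-specific and weight-based: 35% and 50% index, 20% and 5% at 7 days.

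The stated 94% power belongs to 20% vs 5%. With 115 per arm, two-sided 0.05 and a pooled-variance test:

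- null standard error = √(2 × 0.125 × 0.875 / 115) = 0.0436
- alternative standard error = √((0.20 × 0.80 + 0.05 × 0.95) / 115) = 0.0425
- power = Φ((0.15 − 1.96 × 0.0436) / 0.0425) = Φ(1.52) = 93.6%

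So the protocol planned a 7-day outcome that leaves index admissions out.

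**Size of the distortion in the 0/1/2+ count (illustration)**

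Let a be the index admission rate, b the 7-day rate without index admissions, and u the proportion with both. The documents do not give u, so it runs from 0 (no overlap) to b (every 7-day admission is in an index-admitted patient).

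- In category 1 or 2+ under the rule: a + b − u
- Share of these there for the index admission alone: (a − u) / (a + b − u), which falls as u rises

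| Overlap | Patient-specific (a = 0.35, b = 0.20): in 1 or 2+ | index-only share | Weight-based (a = 0.50, b = 0.05): in 1 or 2+ | index-only share |
|---|---|---|---|---|
| None | 55.0% | 0.35/0.55 = 63.6% | 55.0% | 0.50/0.55 = 90.9% |
| Independent | 48.0% | 0.28/0.48 = 58.3% | 52.5% | 0.475/0.525 = 90.5% |
| Full | 35.0% | 0.15/0.35 = 42.9% | 50.0% | 0.45/0.50 = 90.0% |

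Pooled over equal arms, the index-only share is (0.35 + 0.50)/(0.55 + 0.55) = 77.3% with no overlap and (0.15 + 0.45)/(0.35 + 0.50) = 70.6% with full overlap. Mixed cases (full in one arm, none in the other) give 72.2% and 76.2%, inside that range.

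With 115 per arm, about 40-63 and 58-63 patients would be in category 1 or 2+. The planned 7-day rates correspond to 23 and about 6.

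**The case against.** **The sentence may mean something narrower.** It speaks of patients going straight from ED discharge to the hospital, and elsewhere the SAP lists discharge home, admission and observation as separate dispositions. It might cover only patients discharged and then taken to a hospital, some of whom would fit the 4.2 hospitalizations row. This reading is strained: SAP 4.1 uses the term discharge score for the end-of-visit score even when the patient is admitted. It would not settle matters either, because the count would then have no rule for ordinary direct admissions, although its window opens when the patient leaves the ED.

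**The protocol does not expressly exclude index admissions.** This stands. Its endpoint wording (sections 10 and 11) refers only to events within seven days of the visit. Section 12.6 separates the index hospitalization from later ones, but only for defining serious adverse events. The support from the protocol is an inference from its rates; the explicit conflict is inside the SAP.

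**The comparator is a planning rate.** This also stands. The 20% and 5% apply to all patients in an arm. SAP 4.2 would split patients by index status and drop those still in hospital, so it would not produce those figures.

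**It is one descriptive summary.** Largely true. The rule sits in the notes on analyses, is attached to a single categorization, and has no row of its own in Table 17.1. A total that includes index admissions is a legitimate summary, but 7.7.2 does not label it as one.

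**Section 4 already takes precedence.** Not quite. SAP 6.2 ("Except for the primary, secondary endpoints and safety outcomes for which we pre-specified methods to use in section 4") exempts those endpoints from the default tests; it does not rank conflicting definitions. Section 4.2 contains no 0/1/2+ categories, so 7.7.2 is the only instruction for them.

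**Conclusion.** The conflict is real and should be fixed, but its reach is narrow. For the 0/1/2+ count, SAP 7.7.2 contradicts SAP 4.2, the synopsis, the figure titles and Table 17.1. Under the protocol's planning rates, 71-77% of the patients shown with at least one hospitalization would be there only because of the index admission. That range rests on planning assumptions, equal arms and an unknown overlap. By arm it is 43-64% (patient-specific) and 90-91% (weight-based), so one cannot say that index admissions dominate the patient-specific arm whatever the overlap.

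A reader might infer that the tested 7-day endpoints would lose their planned difference or their 94% power, or that every patient in the re-hospitalization row would become an event. The documents do not support this. No passage carries the counting rule into the binary cut at zero, the Poisson model or the composite, and the re-hospitalization row is defined as following discharge from the index stay. The SAP 4.2 endpoints remain sound as defined there, and the primary endpoint and sample size are not involved.

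**What to change.** In SAP 7.7.2, take one of two routes:

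1. Delete the sentence, and state that an admission directly from the index ED visit is not an event in any 7-day return outcome (hospitalizations, re-hospitalizations, the 0/1/2+ count, the composite).
2. Keep the count only as a separately labelled descriptive total that includes index admissions, distinct from the 7-day return endpoints.

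Under either route, state how a patient who moves from observation status to inpatient care is classified, since observation is a disposition of its own and such a patient could now be coded either way.

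The cost is a few sentences, to be settled before unblinding. The split in SAP 4.2 already requires index and later admissions to be told apart, so no new data item should be needed. The case report form is not among the documents, so confirm that it records the two separately.
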